- Resistant disease: Failure to achieve a complete remission (CR, CRc, or CRi) or partial remission. Patients who survive ≥ 7 days following completion of initial treatment, with evidence of persistent leukemia by blood and/or bone marrow examination.

- Death in Aplasia: Patients who survive ≥ 7 days following completion of initial treatment, but die while cytopenic, with an aplastic or hypoplastic marrow obtained within 7 days of death, without evidence of persistent leukemia
- Death from Indeterminate cause: Patients who die before completion of treatment or < 7 days following completion of initial treatment; patients who die ≥ 7 days following completion of initial treatment with no peripheral blood blasts, but no bone marrow examination is available; patients who fail to complete the first cycle of therapy

Relapse

Relapse is defined as:

- Evidence of morphologic relapse with the reappearance of leukemic blasts in the peripheral blood, blasts with Auer rods, $\geq 5\%$ blasts in the bone marrow, or evidence of extramedullary disease not attributable to any other cause. In the setting of recent treatment, if there are no circulating blasts and the bone marrow contains 5-20% blasts, a bone marrow biopsy should be repeated within 1 week to distinguish relapse from bone marrow regeneration.
- The reappearance of cytologically proven extramedullary disease also indicates relapse. Reappearance of a cytogenetic abnormality is considered a cytogenetic relapse. Evidence of bone marrow morphologic involvement or extramedullary disease required.

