6. EFFICACY ANALYSES

Assessment of clinical response will be made according to the International Working Group criteria for AML {Cheson 2003}, which is documented in Appendix 5 of the study protocol. The major criteria for judging response assessment include physical examination and examination of blood and bone marrow.

Efficacy analysis will be presented by treatment group, phase, and dose level, treatment arm, or cohort if applicable, as elaborated in Table 3-2 in Section 3.2. In addition, the pooled analyses of Group C for efficacy specified in Sections 6.1, 6.2, and 6.3 will be present by dose level and total as elaborated in Table 3-3 in Section 3.2. Summaries will be provided for the FAS.

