The category “Other” includes 2 subcategories: Treatment Failure [TF] and No Assessment Done. All subjects in “Other” will be considered as nonresponders and will be included in the denominator when calculating the remission rates per best overall response.

As a sensitivity analysis, complete remission rate, composite complete remission (CR/CRi) rate, and overall response (CR/CRi/PR) rate per best overall response ever achieved during the treatment will be summarized for Groups A and B. The category “Other” includes 3 subcategories: Treatment Failure [TF], Early Treatment Assessment [ETA], and No Assessment Done. For subjects who had response assessment but didn’t achieve any of the first 5 categories

listed above as the best overall response, TF will be the best overall response for those who received 2 induction cycles in Group A or received ≥ 2 induction cycles in Group B, and ETA will be the best overall response for those who only received ≤ 1 induction cycle. All subjects in “Other” will be considered as nonresponders and will be included in the denominator when calculating the remission rates per best overall response.

As an example, assuming a subject in Group A received two induction cycles and discontinued all study drugs, if subject achieved PR at end of Cycle 1 but relapsed at end of Cycle 2, the best overall response is PR while the response assessment at induction completion is relapse.

When the date of initiation of SCT/anticancer therapy other than the study treatment is incomplete or missing, the following algorithm will be followed:

- If the day is missing but the month and year are available, then the imputed day will be the last day of the month.
- If day and month are missing but year is available, then the imputed day and month will be 01Jan or the last day of the month for the last adequate disease assessment if they have the same year, whichever is later.

The following subgroup analyses will be provided for primary analysis:

- Age (<60 years, ≥ 60 years; applicable to Groups A and C)
- Age (≤ 75 years, >75 years; applicable to Group B)
- ELN risk group (Favorable, Intermediate -I, Intermediate -II, Adverse)
- De novo and Secondary AML
- Age and ELN risk group (applicable to Group A)
- With and without MLL
- FLT3-ITD mutation (applicable to Groups A and B)
- NPM1 mutation (applicable to Groups A and B)

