6.2. Secondary Efficacy Endpoints

6.2.1. Definition of Secondary Efficacy Endpoints

- Event free survival (EFS) - defined for all subjects and it is measured from the start of the study therapy until the date of treatment failure, AML relapse or death from any cause, whichever occurs first
- Overall survival (OS) – defined as the interval from the start of the study therapy to the death from any cause

Every attempt will be made to ensure that complete death dates are recorded. In those rare instances where complete death dates are not recorded, the following algorithm will be used:

- If day is missing but the month and year are available, then the imputed day will be the first day of the month or the last known alive date + 1, whichever is later.
- If day and month are missing but year is available, then the imputed date will be 01Jan of that year or the last known alive date + 1, whichever is later.

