6.2.2. Analysis of the Secondary Endpoints

Subjects will be considered as treatment failure if having at least one efficacy assessment prior to SCT and other anticancer therapy (excluding SCT and conditioning regimen) but none of these efficacy assessments is CRc, CR, CRi, or PR; date of treatment failure will be the date of last adequate efficacy assessment prior to SCT and other anticancer therapy (excluding SCT and conditioning regimen). The events and censoring rules are detailed in [Table 6-1](#). Of note, other anti-cancer therapy excludes SCT and conditioning regimen in this table, and the criteria are hierarchical: subjects who meet the criteria on the top will be excluded from the criteria on the bottom.

Table 6-1. Event/Censoring Rules for EFS

Criteria	Event or Censored	Date of Event/Censoring
Relapse, no other anti-cancer therapy or prior to the start of other anti-cancer therapy, and 
 • had SCT prior to relapse, OR • no SCT prior to relapse, and days from last response assessment prior to relapse to relapse was within the following window (2 consecutive response assessments): For Group A: — ≤60 days (2 cycles (including the time waiting for	Event	Date of first relapse

count recovery) + 4 days) if didn't receive post-remission cycle
 
— <=120 days (4 cycles + 8 days) if received post-remission cycle but didn't receive ENTO mono maintenance cycle
 
— <=240 days (8 cycles + 16 days) if received ENTO mono maintenance cycle
		

For Group B:
 
— <=120 days (4 cycles + 8 days) if didn't receive maintenance cycle
 
— <= 240 days (8 cycles + 16 days) if received maintenance cycle
 
For Group C:
 
— <= 60 days (2 cycles + 4 days) if received <= 2 cycles
 
— <= 120 days (4cycles + 8 days) if received 3-4 cycles
 
— <= 240 days (8 cycles + 16 days) if received > 4 cycles
		

Treatment failure, and days from last response assessment prior to treatment failure or first dosing date, whichever is later, to treatment failure was within the window defined above
	
Event
	
Date of treatment failure

Death without treatment failure/relapse/other anti-cancer therapy, and
 
 • had SCT, OR • no SCT, and days from the date of last assessment or first dosing date, whichever is later, to the date of death was within the window defined above 	
Event
	
Date of death

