
No postbaseline assessment, no death
	
Censored
	
Date of first dose

No treatment failure/relapse/death
	
Censored
	
Date of last response assessment (and prior to other anti-cancer therapy if any) or first dosing date, whichever is later

Other anti-cancer therapy started prior to treatment failure/relapse/death	Censored	Date of last response assessment prior to other anti-cancer therapy or first dosing date, whichever is later
Days from last response assessment prior to treatment failure/relapse/death or first dosing date, whichever is later, to treatment failure/relapse/death was not within the window defined above	Censored	Date of last response assessment prior to treatment failure/relapse/death or first dosing date, whichever is later

Censoring Rules for OS:

- For a subject who is not known to have died by the end of study follow-up, OS is censored on the date the subject was last known to be alive.

For EFS or OS in months, the calculation is based on the following formula:

$$(\text{date of event/censoring} - \text{date of first dose} + 1) / 30.4375.$$

EFS and OS will be analyzed using Kaplan-Meier (KM) methods. The KM estimate of the survival function will be computed and the results will be presented using KM curves. The median will be provided along with the corresponding 95% CI. Additionally, the 25% and 75% percentiles for these endpoints will also be provided.

Follow up time for OS will be summarized as continuous variable with descriptive statistics.

- For a subject who is not known to have died by the end of study follow-up, duration of OS follow up in months = $(\text{date of last known to be alive} - \text{date of first dose} + 1) / 30.4375$
- For the remaining subjects, duration of OS follow up in months = $(\text{date of follow-up cutoff} - \text{date of first dose} + 1) / 30.4375$

Data listing for EFS and OS will be presented.

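### SAP Table 6-1 censors EFS at first dose for unassessed subjects who are alive, switched therapy first, or died outside the window without SCT, although Appendix 5 lists failure to complete the first cycle under treatment failure

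*SAP*

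**What the plan says.** - In SAP 6.2.1 the endpoint is "defined for all subjects and it is measured from the start of the study therapy until the date of treatment failure, AML relapse or death", whatever the cause. Treatment failure is therefore an event, and no treated subject is outside the definition.
- SAP 6.2.2 then narrows failure: "Subjects will be considered as treatment failure if having at least one efficacy assessment prior to SCT and other anticancer therapy", with no remission or partial remission among those assessments. A subject with no assessment cannot be a failure.
- Table 6-1 has the row "No postbaseline assessment, no death", censored at first dose. Two lower rows cover other anticancer therapy started first and events outside the window. Both censor at the last assessment or first dose, whichever is later, which for an unassessed subject is first dose.
- A higher row makes death an event if there was no other anticancer therapy and the subject either had SCT or met this condition: "no SCT, and days from the date of last assessment or first dosing date, whichever is later, to the date of death was within the" tabulated window. The table is hierarchical: "subjects who meet the criteria on the top will be excluded from the criteria on the bottom".
- SAP section 6 assesses response by the International Working Group criteria, "which is documented in Appendix 5 of the study protocol". Under Treatment Failure, that appendix includes "patients who fail to complete the first cycle of therapy". The clause stands last in a sub-class headed Death from Indeterminate cause.
- In SAP 6.1.2, subjects in the category No Assessment Done "will be considered as nonresponders and will be included in the denominator when calculating the remission rates".
- SAP 6.5 declares only two changes from the protocol's efficacy analyses, on time to blast clearance and on MRD.

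**The concern.** A subject who stops in the first weeks without a response assessment is likely to be an early failure. Censoring on Day 1 assumes that this subject would have fared like those who stayed. If the gap is informative, the EFS curve is too high. The same subject is a nonresponder in the primary table and contributes nothing to EFS.

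Exposure differs by group. In Group C the first on-treatment marrow is Cycle 1 Day 28. In randomized Group B the Cycle 0 Day 5 marrow is taken only if circulating blasts have cleared, so subjects with persisting blasts wait until Cycle 2 Day 28. SAP section 1 cites a lack of responses to monotherapy, which makes early stopping in Group C plausible. In Group A, Group B Phase 1b and the azacitidine run-in, protocol section 3.1 schedules an end-of-lead-in marrow for everyone, so few subjects should be affected.

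**Working it through.** The documents give no sample size, event target or power for EFS, so there is no plan figure to reproduce.

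**1. Tracing a subject with no post-baseline assessment through Table 6-1**

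| Course after first dose | Result |
|---|---|
| Alive, no other therapy | Censored at first dose |
| Starts other anticancer therapy, then alive or dead | Censored at first dose |
| Dies outside the window, no SCT, no other therapy | Censored at first dose |
| Dies within the window, no other therapy | Event at death |
| Dies after SCT, no other therapy | Event at death |

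For a subject who stops early, the window runs from first dose: 60 days in Group A (no post-remission cycle), 120 days in Group B (no maintenance) and 60 days in Group C (two cycles or fewer). A subject censored at first dose has an EFS time of 1/30.4375 = 0.033 months.

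**2. Effect on the curve**

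Let k of N subjects be affected, f = k/N. Censored on Day 1, they leave before any other event, so the SAP curve is that of the other N − k subjects. Counted as events, they give

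S_event(t) = (1 − f) × S_SAP(t), so S_SAP(t) = S_event(t)/(1 − f).

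This is exact when they are events on Day 1 and nobody else has left by then. Dating them at last dose changes mainly the early part of the curve.

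With S_event = 40%:

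- f = 10%: 0.40/0.90 = 44%
- f = 20%: 0.40/0.80 = 50%
- f = 30%: 0.40/0.70 = 57%

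**3. Direct Kaplan-Meier check**

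The other N − k subjects were given event times at evenly spaced quantiles of an exponential curve with a 6-month median, without censoring. The curve was read at 6 months, with the k subjects censored on Day 1 or counted as events on Day 1.

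| N | k | SAP rule | As events | Ratio = (N − k)/N |
|---|---|---|---|---|
| 54 | 3 | 49.0% | 46.3% | 0.944 |
| 20 | 2 | 50.0% | 45.0% | 0.900 |
| 20 | 4 | 50.0% | 40.0% | 0.800 |
| 12 | 2 | 50.0% | 41.7% | 0.833 |

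The SAP value equalled the value with the k subjects deleted in every case. Under an exponential curve the median is multiplied by 1 + log2(1 − f) when they become events: 0.85 at f = 10% and 0.68 at f = 20%.

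**4. Plausible f in small columns**

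Cohort C3 closed at 12, so two such subjects are 2/12 = 17%. For C1A the protocol gives 15 subjects. SAP 1.2 gives 6, pooled with 9 from Phase 1b who had at least 21 days of drug. In a column of 6, one subject is 1/6 = 17%. Those 9 cannot include anyone who stopped before 21 days of drug.

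**5. Timing in randomized Group B**

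Five lead-in days plus 2 × 28 = 56 days puts Cycle 2 Day 28 at about study Day 61. A subject can complete Cycle 1 and stop before that with no assessment. The Appendix 5 clause does not cover this subject, so failing to complete the first cycle and having no assessment are different sets.

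**The case against.** A reader might infer that every subject who stops without an assessment is censored on Day 1. The table does not say so. The row excludes deaths, and the higher death row makes many early deaths events.

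A reader might also take Appendix 5 as a plain rule that any living subject who misses the first cycle is a failure. Its clause sits under a heading about death. The neighbouring clauses speak of patients who die and this one does not, so it is not worded as limited to deaths, but its reach needs clarifying.

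Nor is an assessment necessarily a marrow. SAP section 6 also names physical examination and blood, and Appendix 5 lets persistent leukemia be shown by blood. Group C has hematology on Cycle 1 Days 8 and 14, so a subject stopped for rising blasts may have a blood-based assessment and be a failure event. The documents do not settle this. Protocol 6.4.2 also requires end-of-treatment procedures before new therapy, including a marrow unless one was done in the previous two weeks. Nothing in the documents shows how often these are missed, so f may be small.

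Protocol 8.5.2 censors event-free subjects at the last available assessment, and first-dose censoring is a natural reading when there is none. The undeclared departure is therefore the narrower failure definition, not the censoring row itself. It is also not a contradiction in itself to be a nonresponder in a proportion and censored in a survival analysis.

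EFS is descriptive, OS counts all deaths, and by-subject listings make affected subjects traceable. These points limit the scope and weight. They do not remove the mismatch with Appendix 5 or the upward direction of the effect.

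**Conclusion.** The point holds in limited form. The three courses censored at first dose in the trace remove likely early failures from the risk set. The failure definition that permits this is narrower than the protocol criteria the SAP adopts, and it is not declared.

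The reported EFS equals the estimate with these subjects as events divided by (1 − f). This rests on treating them as failures and on an assumed f, with 10% to 30% shown only to give the scale. The effect should be largest in Group C and randomized Group B, and small where an end-of-lead-in marrow is scheduled for all. No alpha, power or sample size is affected. It should be corrected, but it does not threaten the primary analysis.

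**What to change.** In SAP 6.2.2 and Table 6-1:

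1. Count a subject who stops study treatment before completing the first cycle, with no post-baseline assessment, as a treatment-failure event dated at the last dose of study treatment. State that the Appendix 5 clause is applied to living subjects, and what counts as an assessment.
2. Keep first-dose censoring of these subjects as a sensitivity analysis.
3. Add a second sensitivity analysis that counts as events all other unassessed subjects who stopped treatment or started other anticancer therapy, for example Group B subjects who finish Cycle 1 but stop before Cycle 2 Day 28. Starting other therapy is not part of the EFS definition, so it belongs here and not in the main analysis.
4. Report the number of such subjects per table column.
5. Declare in SAP 6.5 any departure from Appendix 5 that is kept.

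The cost is SAP wording and a small derivation from dosing dates already collected. EFS becomes slightly less favourable, and a few withdrawals unrelated to disease will count as failures.

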6.5. Long Term Follow-up

Long term follow-up for survival will be conducted every 6 months (\pm 4 weeks) after the End of Study Treatment visit for up to 3 years (since the start of study therapy). Information to be gathered includes leukemia treatments, other malignancies, and survival. This follow-up can be done during a routine clinic visit, other contact with the subject, or via telephone. Gilead reserves the right to discontinue or shorten the duration of participation in the long term follow-up period at any time. See section [9.3.4](#) for details regarding study discontinuation.

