Remission duration will be analyzed using cumulative incidence by considering competing risks. Relapse (the first situation in [Table 6-2](#)) is considered as the event of interest. Death without relapse (the second situation in [Table 6-2](#)) is a competing risk as death eliminates the occurrence of relapse. The other situations described in [Table 6-2](#) are considered as censored. There are three statuses: 0=censored, 1=relapse, and 2=death without relapse. SAS 9.4 PROC LIFETEST with statement TIME and option EVENTCODE=1 will be used. The estimates of the cumulative incidence of relapse (CIR) at 1, 3, 6, 12, 18, and 24 months (if appropriate) will be reported with the associated 95% CIs.

TTR will be summarized using descriptive statistics.

Data listing of TTR, RFS, and remission duration will be presented.

TTC will not be analyzed as data are not intensively measured/collected.

MRD rates will not be summarized as data are not measured/collected at all visits. A by-subject listing of MRD level will be provided.

The number and percentage of subjects who underwent SCT will be summarized and the corresponding 95% exact CI will be presented. In addition, the same analysis will be performed for subjects who underwent SCT at induction completion, post-remission, and maintenance completion, if applicable. A by-subject listing of SCT will be provided.

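### SAP Tables 6-1 and 6-2 make the censoring of transplanted responders depend on their later outcome: events after SCT count whenever they occur, but event-free time after SCT normally does not

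*SAP*

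**What the plan says.** The EFS rules are in SAP 6.2.2, Table 6-1.

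- **Relapse.** The row has two branches. One is "had SCT prior to relapse, OR" and carries no time limit. The 60-, 120- and 240-day windows sit only in the branch for subjects without SCT.
- **Death.** The row that opens "Death without treatment failure/relapse/other anti-cancer therapy, and" is built the same way: subjects with SCT qualify without a window.
- **SCT does not censor.** The table states that "other anti-cancer therapy excludes SCT and conditioning regimen in this table".
- **Order.** The rows are hierarchical: "subjects who meet the criteria on the top will be excluded from the criteria on the bottom". A late event after SCT is settled near the top and never reaches the out-of-window censoring row.
- **No event.** The censoring date is "Date of last response assessment (and prior to other anti-cancer therapy if any) or first dosing date, whichever is later". There is no SCT branch and no use of the last contact.

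Table 6-2 (SAP 6.3.2) applies the same rules to RFS. CIR takes its coding from that table: "There are three statuses: 0=censored, 1=relapse, and 2=death without relapse".

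Protocol 6.5 sets a contact every 6 months for up to 3 years from the start of therapy. "Information to be gathered includes leukemia treatments, other malignancies, and survival". On how it is done: "This follow-up can be done during a routine clinic visit, other contact with the subject, or via telephone". OS, by contrast, is censored at the date last known alive. Protocol 8.5.2 censors EFS at the last available assessment and has no SCT rule.

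**The concern.** SCT is an intended route for responders in Groups A and B (Protocol 3.1.2 to 3.1.4). Scheduled marrows follow treatment cycles, remission or relapse, and the end of study treatment (Protocol 6.3, 6.4.2 and Appendix 2). None is scheduled after SCT. For a transplanted responder who stays well, the last response assessment is therefore normally close to the transplant, although the 6-monthly contacts may show the subject alive much later.

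A transplanted responder who relapses or dies stays at risk up to that event. Whether a subject is counted at risk after transplant then depends on what happens later. Kaplan-Meier and cumulative incidence estimates both require that it does not. EFS is a secondary endpoint reported with median and quartiles, and RFS and CIR inherit the rule. Because successful transplants lose their event-free time, the distortion grows with the number of subjects bridged to SCT.

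**Working it through.** The documents state no EFS, RFS or CIR figure to reproduce. The window lengths do reproduce: 2×28+4 = 60, 4×28+8 = 120 and 8×28+16 = 240 days.

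**1. Two subjects traced through Table 6-1.** Both are responders, last assessed and transplanted at month 3, with no other anti-cancer therapy. One dies at month 30: the death row applies, an event at month 30. The other is alive and relapse-free at a month-36 contact: the no-event row applies, censored at month 3.

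**2. Mechanism in transplanted subjects alone.** Take 20 transplanted subjects: 8 with events spread evenly over months 5 to 24, and 12 event-free to month 36 but last assessed at month 3.

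- SAP rule: after month 3 only the 8 remain at risk. Three events by month 12 give 5/8 = 62.5%; all 8 by month 24 give 0%.
- Follow-up used for everyone: 17/20 = 85% and 12/20 = 60%.

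In closed form, let F(t) be the event probability by month t, with a constant hazard from month 3. Symmetric follow-up gives 1 − F(t); the SAP rule gives 1 − F(t)/F(36).

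- F(36) = 0.30: hazard = −ln(0.70)/33 = 0.0108 and F(24) = 0.203. EFS at 24 months is 80% symmetric and 1 − 0.203/0.30 = 32% under the SAP rule.
- F(36) = 0.50: F(24) = 0.357. EFS is 64% symmetric and 1 − 0.357/0.50 = 29% under the SAP rule.

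**3. Whole-group illustration.** From the documents: n = 40 (Group A Phase 2), CR/CRi 70% (lowest assumed rate in SAP Table 1-2), follow-up to 36 months. Assumed, because the documents do not say:

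- 25%, 50% or 75% of responders transplanted at month 3, last assessed at months 2.5 to 2.9;
- 40%, 60% or 80% event-free 24 months after SCT, every post-SCT event captured;
- median 12 months to event in other responders;
- nonresponders fail at months 1.5 to 2;
- for CIR, half of post-SCT events and 85% of other events are relapses.

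Mean 24-month EFS over 2,000 simulated trials, SAP rule versus symmetric follow-up (difference in points):

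| Responders transplanted | 40% event-free | 60% event-free | 80% event-free |
|---|---|---|---|
| 25% | 18.5 vs 22.1 (3.6) | 19.2 vs 25.3 (6.1) | 19.6 vs 28.8 (9.2) |
| 50% | 17.7 vs 24.9 (7.2) | 19.6 vs 31.8 (12.2) | 20.4 vs 38.3 (17.9) |
| 75% | 16.8 vs 28.0 (11.2) | 19.7 vs 38.2 (18.5) | 21.6 vs 48.1 (26.5) |

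At 12 months the EFS differences are 2 to 14 points. The 24-month CIR among responders is 4 to 28 points higher under the SAP rule; in the middle cell it is 54.8% against 41.6%.

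**4. Low end.** A variant with 12 treatment failures, 28 responders, 30% to 50% post-SCT events by month 36, and other responders followed to month 19:

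- 3 transplanted, none assessed after SCT: 24-month gap about 4 to 5 points.
- 7 to 14 transplanted, with 80% of the event-free ones having a late post-SCT assessment: about 1 to 2 points.

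**The case against.** Several objections limit the point.

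- **Unscheduled assessments.** A reader might infer that time after SCT enters the analysis only for subjects with an event. The tables do not say so. The no-event row is not restricted to assessments before SCT, so a recorded post-SCT assessment extends event-free time. The protocol also asks sites to try to keep subjects in follow-up. This stands. None is required, though, so the result would depend on site practice.
- **Missed relapses.** Relapse is not among the items listed for long-term follow-up. If it goes unrecorded and new therapy starts, Table 6-1 censors the subject before that therapy, even if death follows. This stands and reduces the number of late events assumed above. It does not restore the lost event-free time.
- **Curves not planned.** The 32% and 0% figures describe transplanted subjects alone. The SAP plans no EFS curve by SCT status, so they show the mechanism and not a result that will be reported.
- **Direction.** A reader might infer that whole-group EFS must come out too low. The out-of-window row drops late events in non-transplanted subjects and pushes EFS upward, so the net sign depends on the data. That is a second problem and does not correct the first.
- **Inputs.** SCT may follow several post-remission or maintenance cycles, so last marrows may be later than month 3. SAP section 1 says the study will end early, and Protocol 6.5 lets the sponsor shorten follow-up.
- **Redaction.** Parts of SAP 6.3 are blacked out, so an SCT sensitivity analysis for RFS or CIR cannot be ruled out. SAP 6.2.2 is readable and has none for EFS.

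**Conclusion.** The rule is wrong as written for transplanted responders: their censoring depends on their later outcome. It biases their contribution to EFS and RFS downward and to CIR upward. Subjects without a response before SCT are normally treatment failures already, so they are little affected. The documents describe no SCT pathway for Group C.

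No single size can be given, because the number transplanted, the timing of the last marrow and the length of follow-up are not stated. Under the assumptions shown, the whole-group difference in 24-month EFS runs from about 1 to 5 points to about 27 points, before any opposite effect of the out-of-window row.

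This should be fixed but does not put the trial's main conclusions at risk. EFS is a descriptive secondary endpoint, and RFS and CIR are exploratory. Group A and B response at induction completion uses assessments before SCT, and OS uses the date last known alive.

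**What to change.** 1. Add a row to Tables 6-1 and 6-2 for subjects who had SCT and have no relapse, death or other anti-cancer therapy. Censor them at the last long-term follow-up contact at which they were alive with no new leukemia treatment recorded. Because the tables are hierarchical, place the row above the existing no-event row.
2. Add a sensitivity analysis that censors every transplanted subject at the SCT date. It treats events and non-events alike but estimates a different quantity and assumes SCT is non-informative. In the simulated scenarios it gave 24-month EFS of about 19% to 21%, close to the SAP rule, so such agreement should not be read as support for that rule.

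The cost is SAP wording and one derivation from data already collected, feasible before database finalization. The downside is that relapse-free status between contacts is inferred from the absence of new leukemia treatment, so an untreated relapse would count as event-free. A new relapse field on the follow-up form is not worth adding in a study that is ending early.
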